#### **12.4.5 Safety laboratory**

Safety laboratory tests (except for urine dipsticks for urinalysis, semi-quantitative urinary ACR determination, urine drug testing, and urine pregnancy testing) will be performed by a central laboratory.

The use of any laboratory facility other than the designated laboratory for safety laboratory tests required by this protocol is not allowed. The only exception is in the case of an emergency where the investigator requires the results quickly.

A table of the reference ranges for each of the laboratory parameters measured with a description of the methods will be provided by the laboratory before the trial start and is to be filed in the investigator's site file.

Changes in the reference ranges or in the methodology during the course of the trial are to be communicated by the laboratory to the sponsor who will inform the investigators.

The trial sites will be provided with a manual by the laboratory specifying the specimen collection, preparation, packaging, and transport of all safety laboratory tests required by this protocol.

Throughout the clinical part of the trial, the investigator must provide a comment in the eCRF regarding the clinical relevance of any laboratory values outside the sponsor-defined alert range.

Results for the laboratory parameters defined below will be sent electronically to the trial site and transferred electronically to the data management provider where these electronic data will be integrated into the clinical database. The clinical database will be transferred to the sponsor.

The following tests will be performed:

---

##### **Hematology panel**

---

Erythrocytes	Leukocytes (including basophils, eosinophils, lymphocytes, monocytes, and neutrophils if a differential count is performed)
Hematocrit	Platelets
Hemoglobin	

---

---

**Clinical chemistry panel**

---

Alanine aminotransferase	Magnesium
Albumin	Parathyroid hormone a
Alkaline phosphatase	Phosphate
Aspartate aminotransferase	Potassium
Bilirubin (total)	Protein (total)
Calcium (measured and albumin-corrected)	Sodium
Creatine kinase	Triacylglycerol lipase
Creatinine	Urea
Gamma glutamyl transferase	Uric acid
Glucose (non-fasted or fasted)	Vitamin D
Lactate dehydrogenase	

---

a) Enrollment Visit only.

The eGFR will be calculated using the 2009 CKD-EPI creatinine equation (Levey et al. 2009).

---

**Urinalysis panel**

---

Dipstick	Semi-quantitative dipstick	Quantitative analysis
Bilirubin	Urinary albumin/creatinine ratio	Albumin (microalbumin)
Erythrocytes		Creatinine
Glucose		Calculated urinary albumin/creatinine ratio
Ketones		
Leukocyte esterase		
Nitrite		
pH		
Protein		
Urobilinogen		

---

If the dipstick test is positive except for pH, glucose or ketones and erythrocytes/leukocytes in menstruating subjects, a microscopic examination of urine sediment will be performed to determine the presence of erythrocytes, leukocytes, epithelial cells, crystals, casts, bacteria, and other findings.

The number of samples and volume per sample collected from each subject for safety laboratory analysis are given in [Table 3](#).

If laboratory values of liver parameters exceed pre-defined ranges (a combination of alanine aminotransferase and/or aspartate aminotransferase greater than 3 times the upper limit of normal and/or bilirubin greater than 2 times the upper limit of normal) after first application of IMP, a standard algorithm to detect and follow-up on potential severe cases of drug-induced liver injury will be applied (see Section [18.2](#)).

## **12.4.6 Physical examination**

After treatment allocation, any clinically relevant changes from the previous visit for physical examination will be documented as adverse events.

## **12.4.7 Urine beta-human chorionic gonadotropin pregnancy test**

Urine samples will be provided by women of child-bearing potential at the specified times and tested locally using a urine  $\beta$ -HCG pregnancy dipstick test.

The results of the dipstick test will be directly entered into the eCRF.

Additional pregnancy tests to those specified may be performed if required by local law or regulations.

Pregnancy testing may be requested from the central laboratory.

## **12.5 Collection of pharmacodynamic data**

### **12.5.1 Bone turnover markers**

Details of the blood sample collection times for the bone turnover markers are given in the schedules of events (Section 1.6). Samples should be collected in the morning after an overnight fast due to diurnal variation and effects of a meal. Serum concentrations will be determined for the following bone turnover markers:

- Bone formation markers:
  - Procollagen type I amino-terminal propeptide.
  - Bone alkaline phosphatase.
- Bone resorption marker:
  - C-terminal telopeptide of type I collagen.

Specific procedures for preparation of serum samples and storage and shipment will be provided to the sites.

## **12.6 Collection of markers for disease severity or progression of CRPS**

### **12.6.1 Soluble interleukin-2 receptor (sIL-2R)**

Details of the blood sample collection times for the analysis of sIL-2R are given in the schedules of events (Section 1.6).

Specific procedures for the preparation of the plasma samples and instructions for storage and shipment will be provided to the sites.

## **12.7 Collection of pharmacogenetic and omics data**

Blood samples for storage and pharmacogenetic and omics testing will be collected into plastic ethylenediaminetetraacetic acid (EDTA) tubes from consenting subjects at the times given in the schedules of events (Section 1.6). The blood samples will be labeled with the trial code and subject

number (and, if appropriate, using a bar code). They will not carry any personal identifier (i.e., single-coded data or double-coded data as described in ICH topic E15 2008).

The blood samples will initially be sent from the trial site to a temporary storage site qualified by the sponsor for short-term storage. The samples will then be transferred in batches from the temporary storage site to the bio-banking facility qualified by the sponsor for long-term storage.

Following extraction of DNA from the pharmacogenetic blood samples, the DNA will be stored in appropriate containers and labeled with a trial code and subject number (and, if appropriate, using a bar code). For omics, the plasma samples will be stored.

They will not carry any personal identifier (i.e., they will be double-coded data as described in ICH topic E15 2008). The DNA samples will be stored at the external bio-banking facility for up to 15 years after completion of the trial (defined as the date of approval of the integrated clinical trial report in the sponsor's document management system) to allow for pharmacogenetic testing. After 15 years of storage, the DNA and plasma samples will be destroyed.

## **12.8 Collection of health economics outcome and work productivity data (US sites only)**

### **12.8.1 Work Productivity and Activity Impairment Questionnaire: CRPS**

History of CRPS including impairments of personal activities, both work-related (e.g., absenteeism/presenteeism) and non-work-related will be captured using the WPAI: CRPS (Section 18.3.9).

The WPAI questionnaire is an instrument to measure impairments in both paid work and unpaid work (Reilly et al. 1993). It measures absenteeism and presenteeism as well as the impairments in unpaid activity because of health problems during the past 7 days.

The WPAI: CRPS will be assessed using the tablet computers maintained at the sites at the time points given in the schedules of events (Section 1.6).

### **12.8.2 Medical resources utilization and health economics data collection**

Medical resource utilization and health economics data will include information regarding hospitalization, emergency room visits, nursing home stays, health care provider (other than trial investigator) contacts, home services, home help, and special devices used due to CRPS-related symptoms and pain. Data will be collected at the time points given in the schedules of events (Section 1.6).

The questions to be asked by the investigator are provided in Section 18.5.

The responses to the questions will be documented on paper and stored as part of the source data. Data will be transcribed into the eCRF by the investigator or delegated site staff.

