### 18.3.9 Work Productivity and Activity Impairment Questionnaire: CRPS

#### WORK PRODUCTIVITY AND ACTIVITY IMPAIRMENT QUESTIONNAIRE: COMPLEX REGIONAL PAIN SYNDROME VERSION (WPAI:CRPS)

The following questions ask about the effect of your **CRPS** on your ability to work and perform regular daily activities. *Please fill in the blanks or circle a number, as indicated.*

1) Are you currently employed (working for pay)?        NO        YES  
*(If NO, check "NO" and skip to question 6)*

The next questions refer to the **past seven days**, not including today.

2) During the past seven days, how many hours did you miss from work because of problems associated with your CRPS? *Include hours you missed on sick days, times you went in late, left early, etc., because of problems associated with CRPS. Do not include time you missed to participate in this study.*  
       HOURS

3) During the past seven days, how many hours did you miss from work because of any other reason, such as vacation, holidays, time off to participate in this study?  
       HOURS

4) During the past seven days, how many hours did you actually work?  
       HOURS *(If "0", skip to question 6)*

5) During the past seven days, how much did **CRPS** affect your productivity while you were working? *Think about days you were limited in the amount or kind of work you could do, days you accomplished less than you would like, or days you could not do your work as carefully as usual. If CRPS affected your work only a little, choose a low number. Choose a high number if CRPS affected your work a great deal.*

Consider only how much CRPS affected  
productivity while you were working.

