**HEALTHCARE UTILIZATION**

**Hospitalization**

1. During the past 12 weeks, were you admitted overnight to a hospital (for more than 24 hours)?

Yes       No [SKIP to 2]       Don't know

1.a. If Yes, how many times were you hospitalized in the past 12 weeks?  (#)

1.b. For each hospitalization (during the past 12 weeks), please provide the diagnosis or reason for hospitalization, number of nights, and admission information if available:

#	Major Diagnosis or Reason for Hospitalization	# of Nights	Admission Date
1			 /  /  DD            MMM            YYYY
2			 /  /  DD            MMM            YYYY
3			 /  /  DD            MMM            YYYY
4			 /  /  DD            MMM            YYYY
5			 /  /  DD            MMM            YYYY
6			 /  /  DD            MMM            YYYY
7			 /  /  DD            MMM            YYYY

Note: Keep the original completed form in the subject file. Transcribe the data to the eCRF. Assure consistency of the data related to reported medical history and adverse events for the subject.  
Version 1.0, 23-Nov-2017 by Grunenthal GmbH for KF7013-04

	Health Economics Outcome Questionnaire Booklet KF7013-04	Page 3 / 26
---	--	-------------

Subject No.

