#### Outpatient Health Care Provider Contact

4. Which of the following types of health care providers have you seen or had a telephone call with in the past 12 weeks on an outpatient basis? Indicate the provider frequency, major diagnosis or reason for visit, and whether care was provided for CRPS-related pain or its symptoms. Please be careful not to double-count services.

#	Provider Type	Used?	# visits in past 12 weeks	# phone calls in past 12 weeks	Major Diagnosis or Reason for Visit/Call
a	Family Medicine, Internist, Primary Care provider	 Yes  No  Don't know			
b	Pain specialist	 Yes  No  Don't know			
c	Psychiatrist	 Yes  No  Don't know			
d	Psychologist	 Yes  No  Don't know			
e	Neurologist	 Yes  No  Don't know			
f	Physician Assistant / Nurse Practitioner	 Yes  No  Don't know			
g	Dentist	 Yes  No  Don't know			
h	Podiatrist	 Yes  No  Don't know			

Note: Keep the original completed form in the subject file. Transcribe the data to the eCRF. Assure consistency of the data related to reported medical history and adverse events for the subject.  
Version 1.0, 23-Nov-2017 by Grunenthal GmbH for KF7013-04

	Health Economics Outcome Questionnaire Booklet KF7013-04	Page 5 / 26
---	---	-------------

Subject No.

#	Provider Type	Used?	# visits in past 12 weeks	# phone calls in past 12 weeks	Major Diagnosis or Reason for Visit/Call
i	Integrated medicine	 Yes  No  Don't know			
j	Chiropractor	 Yes  No  Don't know			
k	Physical therapist	 Yes  No  Don't know			
l	Occupational therapist	 Yes  No  Don't know			

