#### Outpatient Health Care Provider Contact

4. Which of the following types of health providers have you seen or had a telephone call with in the past 12 weeks on an outpatient basis? Indicate the provider frequency, major diagnosis or reason for visit, and whether care was provided for CRPS-related pain or its symptoms. Please be careful not to double-count services.

#	Provider Type	Used?	# visits in past 12 weeks	# phone calls in past 12 weeks	Major Diagnosis or Reason for Visit/Call
a	Family Medicine, Internist, Primary Care provider	 Yes  No  Don't know			
b	Pain specialist	 Yes  No  Don't know			
c	Psychiatrist	 Yes  No  Don't know			
d	Psychologist	 Yes  No  Don't know			
e	Neurologist	 Yes  No  Don't know			
f	Physician Assistant / Nurse Practitioner	 Yes  No  Don't know			
g	Dentist	 Yes  No  Don't know			
h	Podiatrist	 Yes  No  Don't know			

Note: Keep the original completed form in the subject file. Transcribe the data to the eCRF. Assure consistency of the data related to reported medical history and adverse events for the subject.  
Version 1.0, 23-Nov-2017 by Grunenthal GmbH for KF7013-04

	Health Economics Outcome Questionnaire Booklet KF7013-04	Page 10 / 26
---	---	--------------

Subject No. [REDACTED]

#	Provider Type	Used?	# visits in past 12 weeks	# phone calls in past 12 weeks	Major Diagnosis or Reason for Visit/Call
i	Integrated medicine	 Yes  No  Don't know			
j	Chiropractor	 Yes  No  Don't know			
k	Physical therapist	 Yes  No  Don't know			
l	Occupational therapist	 Yes  No  Don't know			

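### Question 4 of the health-economics form omits the Section 12.8.2 exclusion of trial-investigator contacts and has no field for whether care was CRPS-related

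*Protocol*

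**What the plan says.** Protocol Section 12.8.2 lists the resource-use data. After hospital, emergency-room and nursing-home use it names "health care provider (other than trial investigator) contacts, home services, home help, and special devices used due to CRPS-related symptoms and pain". It then states: "The questions to be asked by the investigator are provided in Section 18.5". Answers are written on paper, kept as source, and transcribed into the eCRF.

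In Section 18.5, Question 4 at Visit 2 opens: "Which of the following types of health care providers have you seen or had a telephone call with in the past 12 weeks". The forms for Visits 8, 11, 16 and 17 open almost identically: "Which of the following types of health providers have you seen or had a telephone call with in the past 12 weeks on an outpatient". The instruction that follows reads: "Indicate the provider frequency, major diagnosis or reason for visit, and whether care was provided for CRPS-related pain or its symptoms". The answer table has one row per provider type, with columns for use (yes, no, don't know), number of visits, number of calls, and one free-text diagnosis or reason. Pain specialist and neurologist are among the rows.

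Questions 5 and 6 (home services, devices) are limited to CRPS-related pain. Questions 1 to 3 (hospital, emergency room, nursing home) are all-cause, with a reason recorded for each event.

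Section 12.9 calls the assessment exploratory and says it may feed an economic model. Section 14.1.10 plans descriptive summaries only. Collection is at US sites only.

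**The concern.** The form does not fully collect what the text behind it describes, in two respects.

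First, the exclusion of the trial investigator stands in Section 12.8.2 but not on the form. A subject whose investigator is a pain specialist or neurologist could truthfully report trial visits under that row. The only guard is a general warning against double-counting, which concerns duplicates rather than trial visits. The WPAI in the same protocol does carry such an instruction for missed work time: "Do not include time you missed to participate in this study".

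Second, Question 4 asks "and whether care was provided for CRPS-related pain or its symptoms" but has no column for the answer. When a primary-care row holds several visits, some for CRPS and some not, one free-text reason cannot divide the count.

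The number of trial visits in the recall window changes from one questionnaire to the next. If they are counted, the descriptive trend in outpatient contacts partly reflects the visit schedule. At Week 36, so would any comparison of subjects treated and not treated in Treatment Period B. The miscounted contacts could then enter the economic model.

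**Working it through.** The plan states no figure here to reproduce. The check has two parts.

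**1. Text against form**

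| Section 12.8.2 or question stem | Section 18.5 field |
|---|---|
| Contacts other than with the trial investigator | No such exclusion in Question 4 at Visits 2, 8, 11, 16 or 17 |
| Question 4 stem: was the care CRPS-related? | No yes/no field and no separate counts; one free-text reason per row |
| Home services, home help and devices due to CRPS | Present: Questions 5 and 6 carry the restriction |

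The Question 4 columns repeat at all five visits, so the missing field is not a damaged table.

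**2. Scheduled trial visits inside the look-back**

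Inputs are the nominal days in Section 1.6: Visit 1 between Day -60 and Day -8; Visits 2 to 7 on Days 1, 4, 7, 10, 15 and 43; Visit 8 on Day 85; Visits 9 to 11 on Days 113, 155 and 183; Visits 12 to 15 on Days 186, 189, 192 and 197 (Treatment Period B only); Visit 16 on Day 253; Visit 17 on Day 365. The recall period is 12 weeks = 84 days. A visit counts if it falls from (questionnaire day - 84) up to the day before the questionnaire. The questionnaire visit itself is left out.

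| Questionnaire | Window starts | Trial visits inside | Count |
|---|---|---|---|
| Visit 2, Day 1 | 1 - 84 = Day -83 | Visit 1 | 1 |
| Visit 8, Day 85 | 85 - 84 = Day 1 | Visits 2 to 7 | 6 |
| Visit 8, Day 92 | 92 - 84 = Day 8 | Visits 5 to 7 | 3 |
| Visit 11, Day 183 | 183 - 84 = Day 99 | Visits 9, 10 | 2 |
| Visit 16, Day 253, no Period B | 253 - 84 = Day 169 | Visit 11 | 1 |
| Visit 16, Day 253, Period B | Day 169 | Visits 11 to 15 | 5 |
| Visit 17, Day 365 | 365 - 84 = Day 281 | none | 0 |

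The largest change from Visit 2 to Visit 8 is 6 - 1 = 5, falling to 3 - 1 = 2 if Visit 8 is on Day 92, the end of its +7-day window. At Week 36 the largest difference by Period B status is 5 - 1 = 4. Extra enrollment visits, which Section 11.1.1 allows, would raise the Visit 2 count and shrink the first difference. If trial visits are excluded as Section 12.8.2 says, every count is 0.

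**The case against.** The strongest reply is that the form does not stand alone. Under Section 12.8.2 the investigator asks the questions, is bound by the exclusion stated there, and knows which contacts were trial visits. The WPAI is entered on the site tablet computers, so it needs its own instruction more than an interviewer-led form does. Section 18.5 is also labelled a sample, and eCRF completion guidance may exist. This stands in part: a reader might infer that resource use is certainly inflated, and the documents show only that it can be. It does not remove the gap, because Section 12.8.2 names these questions as the instrument and the exclusion is absent from them.

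A reader might also infer that Section 12.8.2 limits every item to CRPS-related use, so that all-cause Questions 1 to 3 contradict it. The wording does not settle that. The qualifier closes the list and may cover only home services, home help and devices, which Questions 5 and 6 already restrict. Section 12.9 speaks of services used by CRPS patients, and Questions 1 to 3 record a reason per event. The CRPS gap is therefore a contradiction inside Question 4. Its free-text column can hold the answer when all care in a row had one cause, and fails when causes are mixed.

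Two further inferences fail. Nothing in the documents makes unrelated care vary by time point, so unequal distortion over time is shown for trial visits only. And Question 1, "were you admitted overnight to a hospital (for more than 24 hours", is not self-contradictory: the bracket reads as the definition of the overnight stay.

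**Conclusion.** The point holds as a form defect of minor weight. Question 4 lacks an exclusion that the protocol states, and it requests an item for which it has no proper field.

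The possible trial-visit contribution runs from 0 to 6 contacts across the questionnaires, and at Week 36 is 5 with Treatment Period B against 1 without. These are upper bounds for scheduled visits. They assume nominal days except where stated, a strict 84-day recall, and that every trial visit is reported as an outpatient contact.

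It would be wrong to infer a bias between randomized arms: both follow the same schedule through Week 26. Subjects treated and not treated in Treatment Period B are selected by pain score and eligibility, so that comparison was never a randomized one. The protocol promises separate descriptive summaries by Period B status for efficacy and safety data, without naming resource use; the Week 36 difference matters only if resource use is split in the same way. The primary and confirmatory endpoints are untouched.

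**What to change.** On all five visit forms:

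- Add to Question 4 an instruction not to count visits to or calls with the trial investigator, or visits made for this study.
- Add to each Question 4 row a CRPS-related yes/no field, with separate counts of CRPS-related visits and calls.
- Add to Question 1 an exclusion of hospital stays made only for trial logistics, since Section 11.3.1 permits these with the sponsor's prior agreement.

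In Section 12.8.2, state which listed items the CRPS qualifier covers.

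The cost is a revision of the form and the eCRF for US sites. Forms already completed will not be fully comparable with the revised ones, and their free text cannot reliably restore separate counts, so an early change loses least.

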## 12.9 Appropriateness of measurements

### Efficacy assessments

As CRPS is a rare, poorly understood chronic pain syndrome condition with very few adequate and well-controlled trials having been conducted, the proposed outcome measures for this trial have not been formally validated in this population.

The efficacy assessments chosen for this trial reflect the core outcome measures for CRPS clinical trials (COMPACT). These were developed by an international consortium of patients, clinicians, researchers and industry representatives to develop and agree on a minimum core set of standardized outcome measures for use in future CRPS clinical trials in an adult population (Grieve et al. 2017). The key concepts identified were pain, disease severity, participation and physical function, emotional and psychological function, self-efficacy, catastrophizing and PGIC. The final core measurement set included the optimum generic or condition-specific patient-reported questionnaire outcome measures, which captured the essence of each domain.

#### *Numerical rating scale for pain*

The unidimensional 11-point NRS is a recommended method of assessing pain intensity in subjects with various types of chronic pain (CPMP/EWP/252/03 Rev. 1).

On the basis of IMMPACT recommendations for core outcome measures in chronic pain studies, the 11-point NRS was chosen as the primary efficacy outcome measure (Dworkin et al. 2005). The NRS is a standard, widely used tool for the assessment of pain (Dworkin et al. 2008). Average, worst, and current pain intensity will be assessed.

For subject-reported outcomes captured electronically, the system will ensure data integrity by allowing only subjects to enter the data (electronic diary, tablet computer at the site). Electronic subject-reported outcome systems ensure that neither sponsors nor investigators can access and change the data, and subjects cannot enter data retrospectively or in advance, i.e., the timing of entries is controlled and compliance is enforced. Additionally, no data are lost because of illegible handwriting. As required by the FDA Guidance for Industry 2009 on the use of subject-reported outcomes, the database for the electronic patient-reported outcomes uses a regular back-up and does not allow access to unblinded data.

Subjects report little difficulty with electronic patient-reported outcome system procedures and are not unduly burdened by their use resulting in good reporting compliance (Stone et al. 2004).

